9.3.2 Outcomes

The outcomes will be assessed during the post-index period for the two cohorts. If a patient discontinued the index NOAC or switched to a different NOAC, the outcomes assessment would not continue beyond the date of discontinuation or the switch. The primary and secondary outcomes assessed will be safety and effectiveness measures as described below in the [Outcomes of Interest table](#).

The safety and effectiveness analysis will be conducted for the following cohorts:

- Oral Anticoagulant treatment naive patients: Dabigatran vs. Rivaroxaban
- Oral Anticoagulant treatment naive patients: Dabigatran vs. Apixaban

Outcomes of Interest	
Primary	Stroke (hemorrhagic, ischemic, uncertain classification) Major bleeding
Secondary	Major bleeding, by the following sites 
 • Major intracranial • Major extracranial 
 ◦ Major gastrointestinal ◦ Other Stroke by type 
 • Ischemic stroke • Hemorrhagic stroke Transient ischemic attack (TIA) All-cause mortality
Further	[REDACTED]

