Anticoagulants		
Dabigatran	833370302001	8333703020
Argatroban	83337015	8333701500, 8333701520
Warfarin	83200030	8320003020
Heparin	83100020	8310002020, 8310002022, 8310002025, 8310002030, (Also include HCPCS code: Injection, heparin sodium, (heparin lock flush), per 10 units - J1642 , Injection, heparin sodium, per 1000 units - J1644)
Enoxaparin	83101020	8310102010 (Also include HCPCS code: Injection, enoxaparin sodium, 10 mg - J1650)
Tinzaparin	83101080	not exist in GPI database (Include HCPCS code: Injection, tinzaparin sodium, 1000 iu - J1655)
Dalteparin	83101010	8310101010 (Also include HCPCS code: Injection, dalteparin sodium, per 2500 iu - J1645)
Rivaroxaban	83370060	8337006000
Apixaban	83370010	8337001000
Antiplatelet		
Clopidogrel	85158020	8515802010
Brilinta (ticagrelor)	85158470	8515847000
Prasugrel	85158060100330, 85158060100320	8515806010
Ticlopidine	85158080100320	8515808010
Cilostazol	85155516000320, 85155516000330	8515551600
Dipyridamole	85150030000310, 85150030000320, 85150030000330	8515003000
NSAIDs	6610	6610007000, 6610003000, 6610002000, 6610004010, 6610001010, 6610006000, 6610008000, 6610006010, 6610009010, 6610001200, 6610005000, 6610006500, 6610003500, 6610000710, 6610101000, 6610000720, 6610000800, 6610003710, 6610990220, 6610052500, 6610005200, 6610005500, 6610003010, 6610002040, 6610006050, 6610002050, 6610990328, 6610990244, 6610005260, 6610990232, 6610000700, 6610990241, 6610990340, 6610990435, 6610990337, 6610990217, 6610990338, 6610990256, 6610990440, 6610990339, 6610990315, 6610990317,

		6610990238,
--	--	-------------

Table 9. Outcome Codes

Medical Conditions	ICD-9 Codes	Description	ICD-10 Codes
Stroke		Inclusive of ischemic stroke and hemorrhagic stroke below	
Major Bleeding		Inclusive of hemorrhagic stroke, major intracranial bleeding and major extracranial bleeding below	
Ischemic Stroke (Primary Only)	433.x1	Occlusion and stenosis of precerebral arteries with cerebral infarction	I63.xxx
	434.x1	Occlusion of cerebral arteries with cerebral infarction	
	436	Acute, but ill-defined, cerebrovascular disease	I67.89
	Exclusion	EXCLUDE above codes if hospitalization lasted <48 hours and was accompanied by carotid endarterectomy (ICD-9 procedure code 38.1)	
Hemorrhagic Stroke (Primary Only)			
	431	Intracerebral hemorrhage (ICH)	I61.x

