	Exclusion	EXCLUDE above codes if “traumatic brain injury” ICD-9-CM code (800 to 804, 850 to 854) or “rehabilitation care” as the primary ICD-9-CM code (V57) is present.	S02.xxxA, S02.xxxB, S06.xxxA, Z51.89
Major Intracranial Bleeding (Primary or Secondary)	430	Subarachnoid hemorrhage	I60.xx
	431	Intracerebral hemorrhage	I61.x
	432.x	Other and unspecified intracranial hemorrhage	I62.xx
	852.0	Subarachnoid hemorrhage following injury without mention of open intracranial wound	S06.36xA
	852.2	Subdural hemorrhage following injury without mention of open intracranial wound	S06.4XXA
	852.4	Extradural hemorrhage following injury without mention of open intracranial wound	S06.5XXA
	853.0	Other and unspecified intracranial hemorrhage following injury without mention of open intracranial wound	S06.6XXA

	Exclusion	EXCLUDE – above codes if concomitant discharge diagnosis of major trauma was present (ICD-9 codes 852.1, 852.3, 852.5, and 853.1)	S01.90XA, S06.36xA, S06.4XxA, S06.5XxA, S06.6XxA
Major Extracranial		Inclusive of major GI bleeding, major urogenital bleeding and major other bleeding	
Major GI Bleeding		Inclusive of major upper GI bleeding and major lower GI bleeding	
Major upper GI bleed (Primary Only)	531.0x	Acute gastric ulcer with hemorrhage with/without obstruction	K25.0
	531.2x	With hemorrhage and perforation with/without obstruction	K25.2
	531.4x	(chronic or unspecified gastric ulcer with hemorrhage with/without obstruction)	K25.4
	531.6x	(with hemorrhage and perforation with/without obstruction)	K25.6
	532.0x	(acute duodenal ulcer with hemorrhage with/without obstruction)	K26.0
	532.2x	(with hemorrhage and perforation with/without obstruction)	K26.2
	532.4x	(chronic or unspecified duodenal ulcer with hemorrhage with/without obstruction)	K26.4
	532.6x	(with hemorrhage and perforation with/without obstruction)	K26.6
	533.0x	(acute peptic ulcer of unspecified site with hemorrhage with/without obstruction)	K27.0
	533.2x	(with hemorrhage and perforation with/without obstruction)	K27.2
	533.4x	(chronic or unspecified peptic ulcer of unspecified site with hemorrhage with/without obstruction)	K27.4
	533.6x	(with hemorrhage and perforation with/without obstruction),	K27.6
	534.0x	(acute gastrojejunal ulcer with hemorrhage with/without obstruction)	K28.0
	534.2x	(with hemorrhage and perforation with/without obstruction)	K28.2
	534.4x	(chronic or unspecified gastrojejunal ulcer with hemorrhage with/without obstruction)	K28.4

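### In Table 9 the four ICD-10 injury codes that qualify as major intracranial bleeding are also listed as exclusions, so events coded in ICD-10 may be under-counted

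*Combined protocol and SAP*

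**What the plan says.** In the combined protocol and SAP, Annex 1, Appendix A, Table 9 (Outcome Codes), one block has a heading that begins "Major Intracranial Bleeding (Primary or Secondary". Its entries are:

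- **ICD-9, qualifying:** 430, 431, 432.x, and the injury codes 852.0, 852.2, 852.4 and 853.0. All four injury codes are restricted to injuries with no open wound mentioned; for 852.2 the text is "Subdural hemorrhage following injury without mention of open intracranial wound".
- **ICD-9, excluding:** "codes 852.1, 852.3, 852.5, and 853.1".
- **ICD-10, qualifying:** I60.xx, I61.x, I62.xx, S06.36xA, S06.4XXA, S06.5XXA, S06.6XXA.
- **ICD-10, excluding:** "S01.90XA, S06.36xA, S06.4XxA, S06.5XxA, S06.6XxA".

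The rule in the Exclusion row is to drop the "above codes if concomitant discharge diagnosis of major trauma was present".

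Table 9 defines major bleeding as "Inclusive of hemorrhagic stroke, major intracranial bleeding and major extracranial bleeding below". Section 9.3.2 makes major bleeding a primary outcome. It lists intracranial bleeding among the secondary outcomes under "Major bleeding, by the following sites". The Abstract (Data analysis) confirms that both code systems are used.

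**The concern.** A code that qualifies an event should not, by itself, also disqualify it. On the ICD-9 side one set of injury codes brings events in and a separate set takes them out, so some injury-coded bleeds were clearly meant to count. On the ICD-10 side the same four codes do both. Two programmers could implement the row differently, and the most literal implementation cancels part of its own inclusion list.

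What is at stake is a component of a primary outcome. Section 9.7.1 ends the patient-time denominator at the outcome event and reports event rates for each treatment. A missed event therefore lowers the numerator and lets person-time run on. Reported rates would be too low even if both drugs in a comparison were affected equally.

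**Working it through.** The plan gives no figure to reproduce. The check compares code lists, taken from the Major Intracranial Bleeding block of Table 9 and ignoring letter case.

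**Step 1. Overlap of the qualifying and excluding lists.**

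| System | Qualifying | Excluding | In both |
|---|---|---|---|
| ICD-9 | 7 | 4 | 0 |
| ICD-10 | 7 | 5 | 4 (all the injury codes) |

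S06.36xA is printed identically in both places. The other three differ only in letter case (XXA against XxA). Reading a lower-case x as a wildcard gives the same overlap. S01.90XA is the only exclusion code that does not also qualify. The only other Exclusion row in Table 9 with ICD-10 codes, for hemorrhagic stroke, has 1 qualifying and 4 excluding entries and no overlap.

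**Step 2. Which code patterns count as an event.** Three patterns were tried:

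- a lone injury code: 4 cases;
- a non-injury hemorrhage code (430–432, or I60–I62) with an injury code: 3 × 4 = 12 cases;
- two different injury codes: 4 × 3 / 2 = 6 cases.

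| System and reading of the Exclusion row | Lone injury code | Non-injury + injury | Two injury codes |
|---|---|---|---|
| ICD-9 | 4 of 4 | 12 of 12 | 6 of 6 |
| ICD-10, as printed: any listed code excludes | 0 of 4 | 0 of 12 | 0 of 6 |
| ICD-10, *concomitant* = second diagnosis, whole event dropped | 4 of 4 | 0 of 12 | 0 of 6 |
| ICD-10, *concomitant* = second diagnosis, applied code by code | 4 of 4 | 12 of 12 | 0 of 6 |
| ICD-10, S01.90XA together with an S06 code (not stated) | 4 of 4 | 12 of 12 | 6 of 6 |

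In the code-by-code row, I60–I62 with S06 survives because the S06 code still qualifies, whereas two S06 codes knock each other out. A lone I60–I62 code counts on every row (3 of 3). Pairs can arise because the block accepts secondary as well as primary positions.

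**Step 3. Is a lost event recovered elsewhere?** Major bleeding also takes in hemorrhagic stroke, which has I61.x as its ICD-10 code. That row's own exclusion, "S02.xxxA, S02.xxxB, S06.xxxA, Z51.89", covers every S06 code ending in A. An I61.x event with S06 that is dropped from the intracranial block is therefore not restored.

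**Step 4. Effect of deleting the four S06 codes from the exclusion cell.** The three patterns become 4 of 4, 12 of 12 and 6 of 6, as under ICD-9. This removes the self-contradiction but leaves S01.90XA as the whole ICD-10 trauma exclusion, and the documents do not define that code. The ICD-9 exclusion covers 7 × 4 = 28 qualifying-with-excluding pairs; a lone S01.90XA covers 7 × 1 = 7. Whether those 7 stand for the same injuries cannot be judged from the table. If the combination reading was intended, I60–I62 with S01.90XA and no S06 code counts today, and a bare deletion would exclude it (3 of 3 changed).

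**The case against.** The strongest reply is that the cell may be shorthand for S01.90XA occurring with one of the S06 codes. On that reading every pattern tested agrees with ICD-9. Reading the exclusion as limited to codes that do not themselves qualify would also restore agreement for these patterns. There is some support for treating the cell as shorthand: the hemorrhagic stroke row says in words that rehabilitation care must be the primary code, yet its ICD-10 cell lists Z51.89 without that condition. ICD-10 exclusion cells in this table can thus omit logic given in words.

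Part of this stands. A reader might infer that ICD-9 and ICD-10 disagree however the row is read, and that goes too far. But the cell is a plain comma list, and Table 9 writes out *and* where it wants a combination, as in the ICD-10 entry for menstrual bleeding with anemia. If a harmless meaning was intended, the text still has to say so.

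It can also be said that impact is limited. The code-pair counts are checks of logic with equal weight on each pair, not counts of patients. Lone I60–I62 codes are never affected, and if *concomitant* means a second diagnosis a lone S06 code still counts. Section 9.5 calls the analyses descriptive and the tests exploratory. All of this is fair. It bears on how large the effect may be, not on whether the cell contradicts itself.

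**Conclusion.** The concern holds as a coding contradiction that should be fixed. All four ICD-10 injury codes that qualify as major intracranial bleeding also appear as exclusions, against none under ICD-9. As printed, events carrying them cannot count. If *concomitant* means a second diagnosis, events with two listed S06 codes are lost, and so are I60–I62 events with S06 when the exclusion acts on the whole event. Agreement with ICD-9 needs a reading that the table does not state.

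Major intracranial bleeding and major bleeding may therefore be under-counted in ICD-10 time. The number of events cannot be derived: the documents give neither the frequency of S06 coding or co-coding nor the share of person-time under ICD-10.

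A reader might go on to infer bias between drugs. The documents do not support that. The rule is the same for all drugs, and Section 9.7 lists month and year of index date as a candidate propensity score variable. The finding rests only on the printed lists and the Exclusion wording.

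**What to change.** Correct the ICD-10 exclusion cell so that no code by itself both qualifies and disqualifies an event: remove the four S06 codes as stand-alone exclusions. Deletion alone does not establish agreement with ICD-9, so the sponsor should also reconcile the cell with 852.1, 852.3, 852.5 and 853.1 by stating:

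- which ICD-10 code or code combination represents major trauma, including whether S01.90XA applies alone or only with an S06 code;
- whether *concomitant* means a second diagnosis.

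Apply the corrected exclusion to all qualifying codes, including I60–I62, as the ICD-9 side does for 430–432. Then re-run the outcome program for major intracranial bleeding and major bleeding.

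The cost is one table cell, one sentence of definition and a program re-run. No new data are needed.

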Bleeding (includes anemia and other prior hemorrhage)	285.0x, 285.1x, 285.9x, 423.0x, 430.x-432.x, 455.2x, 455.5x, 455.8x, 459.0x, 531.0x, 531.2x, 531.4x, 531.6x, 532.0x, 532.2x, 532.4x, 532.6x, 533.0x, 533.2x, 533.4x, 533.6x, 534.0x, 534.2x, 534.4x, 534.6x, 562.02, 562.03, 562.12, 562.13, 568.81, 569.3, 569.83, 569.85, 569.86, 578.0, 578.1, 578.9, 599.7x, 719.1x, 784.7x, 786.3x; ICD-9 procedure code 44.43; CPT code 43255	D62, D64.0, D64.1, D64.2, D64.3, D64.9, I31.2, I60.xx, I61.x, I62.xx, K25.0, K25.2, K25.4, K25.6, K26.0, K26.2, K26.4, K26.6, K27.0, K27.2, K27.4, K27.6, K28.0, K28.2, K28.4, K28.6, K55.21, K57.11, K57.13, K57.31, K57.33, K62.5, K63.1, K63.81, K64.4, K64.8, K66.1, K92.0, K92.1, K92.2, M25.0xx, R04.0, R04.2, R04.81, R04.89, R04.9, R31.0, R31.1, R31.21, R31.29, R31.9, R58; ICD-10 procedure code: 0W3P8ZZ
Labile INRs		
Elderly (Age >65 years)	-	
Drug or alcohol abuse (1 point for each)	Drug: NSAIDs (GPI codes 6410, 6610), Anti-platelets (8515), Other aspirin-containing products (3940990215, 4399100222, 4399100223, 4399100232, 4399100405, 4399400321, 4399400456, 4399590415, 4399590419, 6030990225, 6499000220, 6499000221, 6499000225, 6499000226, 6499000232, 6499000320, 6499000321, 6499000335, 6499000340, 6499000450, 6499000460, 6499100220, 6499100222, 6499100228, 6499100330, 6499100335, 6599000222, 6599100210, 6599100220, 6599100325, 6599100430, 6599100510, 6599170220, 6599400220, 7599000210, 7599000240, 7599000310, 7599000320, 8515990220, 9990000000)	

	Alcohol: 291.xx, 303.xx, 305.0x, 357.5x, 425.5x, 571.1x, 571.2x, 571.3x; ICD-9 procedure codes 94.61-94.63, 94.67-94.69	F10.xxx, G62.1, I42.6, K70.xx; ICD-10 procedure code: HZ2ZZZZ, HZ30ZZZ, HZ31ZZZ, HZ32ZZZ, HZ33ZZZ, HZ34ZZZ, HZ35ZZZ, HZ36ZZZ, HZ37ZZZ, HZ38ZZZ, HZ39ZZZ, HZ3BZZZ, HZ40ZZZ, HZ41ZZZ, HZ42ZZZ, HZ43ZZZ, HZ44ZZZ, HZ45ZZZ, HZ46ZZZ, HZ47ZZZ, HZ48ZZZ, HZ49ZZZ, HZ4BZZZ, HZ50ZZZ, HZ51ZZZ, HZ52ZZZ, HZ53ZZZ, HZ54ZZZ, HZ55ZZZ, HZ56ZZZ, HZ57ZZZ, HZ58ZZZ, HZ59ZZZ, HZ5BZZZ, HZ5CZZZ, HZ5DZZZ, HZ63ZZZ, HZ83ZZZ, HZ86ZZZ, HZ88ZZZ, HZ89ZZZ, HZ93ZZZ, HZ96ZZZ, HZ98ZZZ, HZ99ZZZ
--	---	---

*the maximum score will be 8 since we do not have data available for labile INRs

After assessing the risk factors and adding up the score, the bleed risk classifications are as follows:

Score	HAS-BLED Bleed Risk Classification
0-1	Low
2	Intermediate
3 or greater	High

Table 8. Atrial Fibrillation Medications

Rate control medications	GPI codes starting with:	GPI 10
Beta blockers	3300	3310004510, 3310004512

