	534.6x	(with hemorrhage and perforation with/without obstruction)	K28.6

	578.0	(hematemesis)	K92.0
	ICD-9 Procedure Code 44.43	(endoscopic control of gastric or duodenal bleeding)	
	CPT code 43255	(upper gastrointestinal endoscopy including esophagus, stomach, and either the duodenum and/or jejunum as appropriate with control of bleeding, any method)	
Major lower GI bleeding (Primary Only)	562.02	Diverticulosis of small intestine with hemorrhage	K55.21
	562.03	Diverticulitis of small intestine with hemorrhage	K57.11
	562.12	Diverticulosis of colon with hemorrhage	K57.13
	562.13	Diverticulitis of colon with hemorrhage	K57.31
	569.3x	Hemorrhage of rectum and anus	K57.32
	569.85	Angiodysplasia of intestine with hemorrhage	K62.5
	578.1x	Blood in stool	K92.1
	578.9	Hemorrhage of GI tract, unspecified	K92.2
Major urogenital bleed (Primary Only)	599.7	Hematuria	R31.0 - R31.29
	626.2x and (280.0, 285.1 or 285.9)	Excessive/frequent menstruation and secondary diagnosis indicating acute bleeding (anemia)	N92.0 and (D50.0, D62, D64.9)
Other major bleeds (Primary Only)	719.1x	Hemathrosis	D62
	423.0x	Hemopericardium	I31.2
	786.3x	Hemoptysis	M25.0xx
	784.7x	Epistaxis	R04.0
	459.0x	Hemorrhage not specified	R04.2
	285.1x	Acute posthemorrhagic anemia	R04.8x, R04.9, R58
TIA (Primary Only)	435.x	Transient cerebral ischemia as the principal (primary) discharge diagnosis	G45.0, G45.1, G45.8, G45.9, G46.0, G46.1, G46.2
[REDACTED]	[REDACTED]	[REDACTED]	[REDACTED]
[REDACTED]		[REDACTED]	
[REDACTED]	[REDACTED]	[REDACTED]	[REDACTED]
[REDACTED]	[REDACTED]	[REDACTED]	[REDACTED]

APPENDIX B: Inclusion and exclusion diagnosis, procedure and CPT codes**Table 1. List of codes for atrial fibrillation**

Study Inclusion DX	ICD9 Diagnosis Codes	ICD10 Diagnosis Codes
Atrial Fibrillation	427.31	I48.0, I48.1, I48.2, I48.91

Table 2. List of codes and descriptions to identify patients with exclusion diagnoses

Study Exclusion DX	ICD9 Diagnosis Codes	ICD10 Diagnosis Codes
Hyperthyroidism	242.x	E05.00, E05.01, E05.10, E05.11, E05.20, E05.21, E05.30, E05.31, E05.40, E05.41, E05.80, E05.81, E05.90, E05.91
Orthopedic Procedures (See also procedure codes)	V43.64, V43.65	Z9664x, Z9665x
DVT	451.xx, 453.xx	I80.xxx, I82.xxx
PE	415.1x	I26.01, I26.09, I26.90, I26.92, I26.99, I27.82
Pericarditis	391.x, 393, 420.x, 423.2, 036.41, 074.21, 093.81, 098.83	A39.53, B33.23, I01.0, I09.2, I30.0, I30.1, I30.8, I30.9, I31.0, I32, M32.12

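### For lower GI bleeding, Table 9 lists K57.32 where Table 7 lists K57.33, so the primary major-bleeding outcome omits the code that fits hemorrhagic colonic diverticulitis

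*Combined protocol and SAP*

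**What the plan says.** Appendix A, Table 9 defines major lower GI bleeding, primary diagnosis only, by eight ICD-9 codes and eight ICD-10 codes. The fourth ICD-9 code, 562.13, is described as "Diverticulitis of colon with hemorrhage". The fifth ICD-10 code stands in the next row, which reads "Hemorrhage of rectum and anus K57.32". K57.33 is not in Table 9, and no wildcard there would cover it.

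Appendix A, Table 7 (HAS-BLED, bleeding row) carries the same diverticular ICD-9 codes: "562.02, 562.03, 562.12, 562.13, 568.81". Its ICD-10 list contains the run "K57.11, K57.13, K57.31, K57.33, K62.5". K57.32 is not in Table 7.

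Table 9 also fixes how the block feeds the larger outcomes:

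- Major GI bleeding: "Inclusive of major upper GI bleeding and major lower GI bleeding".
- Major extracranial bleeding: "Inclusive of major GI bleeding, major urogenital bleeding and major other bleeding".
- Major bleeding: "Inclusive of hemorrhagic stroke, major intracranial bleeding and major extracranial bleeding below".

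Overall major bleeding is one of the two primary outcomes (Section 9.3.2) and the outcome behind the power assessment (Section 9.5).

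**The concern.** The two tables name the same bleeding conditions in ICD-9 and should therefore name the same ones in ICD-10. They do not. If Table 9 is programmed as listed, a follow-up record with K57.33 as primary diagnosis is not a major bleed, although the same code before index counts as bleeding history in HAS-BLED. A record with K57.32 as primary diagnosis is a major bleed, although Table 7 does not treat that code as bleeding.

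Because the ICD-9 list is unaffected, the definition of this one component also differs between ICD-9-coded and ICD-10-coded follow-up. At stake are the reported rates of major lower GI, GI, extracranial and overall major bleeding, and to a lesser degree their hazard ratios.

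**Working it through.** **Step 1. Compare the lists.**

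| | Table 9, lower GI block | Table 7, bleeding row |
|---|---|---|
| Diverticular ICD-9 codes | 562.02, 562.03, 562.12, 562.13 | the same four |
| Other lower GI ICD-9 codes in Table 9 | 569.3x, 569.85, 578.1x, 578.9 | all four present |
| K57 codes | K57.11, K57.13, K57.31, **K57.32** | K57.11, K57.13, K57.31, **K57.33** |
| Other lower GI ICD-10 codes in Table 9 | K55.21, K62.5, K92.1, K92.2 | all four present |

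All 8 Table 9 ICD-9 codes are in Table 7. Of the 8 ICD-10 codes, 7 are in Table 7, and the exception is K57.32. Table 7 is wider and has further codes of its own, but K57.33 is its only K57 code missing from Table 9.

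**Step 2. Set the row alignment aside.** The Table 9 ICD-10 column runs in ascending order and is not matched to the rows. Table 9 shows this itself. Its urogenital block sets 280.0, 285.1 and 285.9 against D50.0, D62 and D64.9, which puts D62 with 285.1. In the block for other major bleeds, however, D62 stands beside 719.1x. So K57.32 standing beside rectal hemorrhage carries no meaning. The discrepancy is K57.32 in place of K57.33.

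**Step 3. Decide which entry is out of line.** The four diverticular rows of Table 9 are all described as hemorrhagic: diverticulosis then diverticulitis of the small intestine, and the same two for the colon. The ICD-9 codes run in parallel (562.0 followed by 2 and 3; 562.1 followed by 2 and 3). In Table 7 the ICD-10 codes do too (K57.1 followed by 1 and 3; K57.3 followed by 1 and 3). In Table 9 the second pair becomes 1 and 2. K57.32 breaks the pattern and leaves 562.13 without the counterpart that Table 7 supplies.

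**Step 4. Size.** The plan states no figure for this component, and the documents do not give the ICD-10-coded share of follow-up or the frequency of either code. For scale, Section 9.5 (dabigatran vs. rivaroxaban) implies:

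- Pairs after 10% loss: 16,000 × 0.9 = 14,400.
- Dabigatran events: 14,400 × 0.82 × 0.031 = 366.
- Total at a rate ratio of 1.22: 366 × (1 + 1.22) = 813.
- Schoenfeld power: Φ(√813 × ln 1.22 / 2 − 1.96) = 80.9%, against the plan's 80%.

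*Omitted K57.33 events (assumptions: 10–30% of major bleeds ICD-10-coded; 1–10% of those hemorrhagic colonic diverticulitis).*

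- Lower end: 0.10 × 0.01 = 0.1% of primary events, about 1 of 813.
- Upper end: 0.30 × 0.10 = 3.0%, about 24 of 813.
- If both arms lose the same proportion, the ratio is unchanged and 3.1 per 100 person-years becomes 3.1 × 0.97 = 3.007 at the upper end.

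*Added K57.32 events (assumptions: such records are not bleeds; 0.1–0.3 per 100 person-years in ICD-10-coded time; 10–30% of follow-up ICD-10-coded; equal rates in both arms).*

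- Within ICD-10-coded time: 0.1/3.1 = 3.2% to 0.3/3.1 = 9.7% extra events.
- Over all follow-up: 3.2% × 0.1 = 0.3% to 9.7% × 0.3 = 2.9%.
- A true ratio of 1.22 at the upper end (0.3 × 0.3 = 0.09 extra per 100 person-years in each arm): (3.1 × 1.22 + 0.09)/(3.1 + 0.09) = 3.872/3.19 = 1.214.

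The same affected records make up a larger fraction of major GI bleeding, which is a subset of major bleeding.

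**The case against.** The best opposing case has four parts.

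**Meaning of the codes.** The documents never define K57.32, and Table 7 gives two unpaired lists, so the link from K57.33 to 562.13 is inferred. This stands as a limit. A reader might infer that non-bleeding diverticulitis admissions will be counted as major bleeds and will pull the comparison toward no difference. The documents do not establish this: it needs a definition of K57.32 that they do not give, similar false-event rates in both arms, and a true difference to dilute. The conflict between the tables does not depend on it.

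**Scope.** A reader might also infer that the primary outcome is wrong for ICD-10-coded events in general. It is not. Only primary-position K57.32 and K57.33 records in ICD-10-coded follow-up are affected.

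**Balance between arms.** Month and year of index date are among the propensity-score variables (Section 9.7), which tends to even out ICD-10-coded time between arms. That limits bias in the ratio, but it balances the start of follow-up rather than its length and cannot correct a misdefined event or an absolute rate.

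**Exploratory status.** Section 9.5 describes the analyses as descriptive, and none of its power figures depends on this code. That lowers the consequence. It does not justify leaving two tables in conflict on a primary outcome when the event rates are themselves a planned result.

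A misread digit in the extracted text cannot be excluded, but nothing points to one.

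**Conclusion.** The point holds in a narrow form. Tables 7 and 9 agree on diverticular hemorrhage in ICD-9 and disagree on one ICD-10 code, and the internal evidence indicates that K57.32 in Table 9 is the erroneous entry. The disagreement is certain. Which entry is wrong is a well-supported inference from the hemorrhage descriptions, the identical ICD-9 lists and the code pattern.

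The size cannot be derived from the documents. On the stated assumptions, omission affects 0.1% to 3.0% of primary events. If K57.32 records are not bleeds, additions amount to about 0.3% to 2.9%, and a ratio of 1.22 would move to about 1.214. The effect on the overall hazard ratio is therefore probably small, and proportionally larger for major GI bleeding. The case for correcting it is that the code enters a prespecified primary outcome and the correction is almost free.

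**What to change.** In Appendix A, Table 9, lower GI block, replace K57.32 with K57.33 so that the list matches Table 7 and its own descriptions. Setting each ICD-10 code beside the row it represents would make such a slip visible.

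Then check the outcome program. Section 6 dates the start of programming rules to 19 October 2016 and of data analysis to 05 December 2016, while the Abstract dates the protocol 15 December 2016, so code may already exist. If K57.32 was used, rerun major lower GI, GI, extracranial and overall major bleeding. The cost is one code in a list, a check of the program and, at most, a rerun on data already held.
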